18 July 2014

Title: Pilot study: randomized, placebo-controlled comparator trial of IV vs oral iron treatment of RLS with Iron deficiency anemia. (IVOR-IDA)

Principal Investigator: [name].

Protocol: IVOR-IDA

Title: Pilot study: randomized, placebo-controlled comparator trial of IV vs oral iron treatment of RLS with Iron deficiency anemia. (IVOR-IDA)

Principal Investigator: [name].

Type of Study: Double-blind comparator of efficacy of oral (ferrous sulfate) vs. Intravenous iron (ferumoxytol) for treatment of the restless legs syndrome (RLS) occurring with iron deficient anemia (IDA)

Supported by: AMAG pharmaceuticals

Summary:

The restless legs syndrome (RLS) (also known as Willis Ekbom Disease) occurs in about 1/3rd of patients with iron deficiency anemia (IDA). Treatment correcting the IDA is expected to also be effective for reducing or eliminating the RLS with IDA. Two accepted treatments for IDA (oral ferrous sulfate, intravenous ferumoxytol) will be compared for efficacy and speed of response for treatment of RLS occurring with IDA (RLS-IDA). In this study 70 RLS-IDA patients will be randomly assigned 35 each to oral or IV iron treatment using double-blind procedures. Primary outcome will be determined at 6 weeks of treatment with a follow-up at 12 months after treatment. Non-responders at 6 weeks after treatment may, if they qualify, have an open-label IV iron treatment and they will be followed with the same evaluations used after the first set of IV iron treatments.

Primary objectives

1. Determine relative effect sizes of standard IV and oral iron treatment of RLS with iron deficiency anemia
2. Determine time course of treatment response

Exploratory hypotheses:

1) Primary exploratory hypothesis: Reduction in RLS-IDA severity measured by the CGI-2 (much or very much improved) will be greater for IV than oral iron treatment at 6 weeks after starting treatment.

2) Secondary exploratory hypothesis: there will be a greater change from baseline in the IRLS score assessing severity of RLS for IV than oral iron treated patients.

Introduction

Background:

Low IRON status is associated with RLS: RLS has been documented to have significant decreased iron concentrations in the substantia nigra [1] and other areas [2]. This has been documented in multiple studies using both MRI [2] [3] [1] and ultrasound [4]. Peripheral

18 July 2014

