Our major problem in testing the treatment benefits for IDA-RLS for either oral or IV iron is that we do not know the actual effect size of either treatment. We have as an initial estimates the effect sizes from clinical experience with oral and IV iron treatment of IDA-RLS. These have to be considered as provisional estimates of effect sizes. Thus, although we have set the sample size to give adequate power to differentiate iv from oral iron treatment assuming these effect sizes, we do not consider the power estimates to be accurate. We feel they give us an adequate sample to establish effect sizes for future studies and to explore possible differential efficacy for the two treatments. The primary goal of the study is, therefore, to assess effect size. Evaluating differences between the treatments is a tertiary goal of this study.

The decision not to do a placebo control is based on the assumption that the treatment effect size can be adequately determined without a placebo. The decision to do a blinded comparator trial is based on the assumption that we will see differences between the treatments that will establish both the effect sizes and the procedures for a larger study to show these differences. We feel it is very important to determine if efficacy of these treatments differ for RLS-IDA in order to develop guidelines for future treatment of this clinically significant condition affecting many with IDA. We have assumed IV iron will be the preferred treatment for RLS-IDA, but we need to first evaluate this in this pilot study and then in a larger adequately powered clinical study.

Drugs used: The treatment doses are those accepted for treatment of RLS and also appropriate for treatment of RLS-IDA. Choosing doses equivalent to those for the treatment of RLS without IDA will allow a comparison with that literature. We will therefore use for oral iron ferrous sulfate 325 mg taken twice a day matching the dose used in the study of oral iron treatment for RLS without anemia [7]. For IV iron we will use ferumoxytol two doses of 510 mg spaced 2 to 7 days apart. This is the FDA approved dose for treatment of IDA with end stage renal disease. This dose matches the iron dosing used in the study of IV iron treatment for RLS without anemia [6], except we will use ferumoxytol provided by the sponsor rather than ferric carboxymaltose used in the prior trial.

Study Design

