The study is a randomized, comparative open label study to evaluate effect size and time course of treatment response for RLS-IAD over 6 weeks with a 46-week follow-up extension. Two medications and placebos will be used with equal random assignment to both groups

- Ferumoxytol intravenous (IV) 1020 mg – 2 vials of 510 mg (IV push, 2-3 mins) each given 2-7 days apart
- Ferrous sulfate 325 mg (oral) tabs morning and evening.
- Placebo: oral vitamin C 500 mg tabs, Saline infusion

Primary outcome is the CGI-2 score at 6 weeks after treatment starts. IV ferumoxytol 1020 mg treatment (2 separate doses 510 mg 2-7 days apart) will be offered to those not significantly responding (CGI-2 scores less than much or very much improved) at 6 weeks after oral-iron treatment and still meeting all requirements for entry to study. All responders will be followed for 12 months after treatment.

Study Objectives

Primary objectives

1. Determine relative effect sizes of standard IV and oral iron treatment of RLS with iron deficiency anemia for the PGI-2/CGI-2 (much and very much improved) and for IRLS scores
2. Determine time course of treatment response for IRLS, PGI-1 and PGI-2 scores

Secondary objectives

1. Estimate survival times for effective treatment (no return to other RLS medications) for 1 year after treatment
2. Evaluate possible predictors of treatment response
 - a. Iron status or iron response
 - b. IRLS severity
 - c. Subject characteristics (age, gender)
 - d. Medical factors affecting iron status

Tertiary/exploratory objectives

1. Evaluate significance of efficacy differences if any between oral and IV iron treatments at 6 weeks after treatment: Hierarchical testing first for the percentage with CGI-2 of much or very much improved and second for change from baseline in the IRLS score.
2. Evaluate efficacy benefits of each treatment for usual outcomes related to RLS morbidity: sleep, fatigue, quality of life, and mood.
3. Compare lymphocytes of RLS-IAD and non RLS-IAD for differences in iron related proteins.

Study Procedures

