The percentage responding will be evaluated for each drug condition to determine overall effect size at 6 weeks after treatment. This will be calculated for the IRLS scale and the PGI as change from baseline and for the CGI with response determined as much or very much improved (scores of 1 or 2). All scores greater than 2 on the CGI are considered to indicate no significant response. The onset of treatment will be described as the percentage showing much or very much improvement at each of the evaluations and by the change in IRLS score from baseline at each evaluation. The duration of treatment over the 12 month follow up will be described as the percentage of responders and the IRLS change from baseline at each time point for both oral and IV iron. The oral iron treatment will be stopped for all subjects at the 6-week time point.

The outcomes for the oral versus IV treatments at 6 weeks will be compared using a standard unpaired unequal variance t-test for the change in IRLS scores from baseline. The number of responders compared to no-responders will be compared using the Fisher Exact test.

Sample Size

Uncontrolled experience observing IDA patients with RLS indicated that about 80% responded to IV iron (about 1000mg dose) and 50% responded to standard oral iron treatment over 6 to 12 weeks. These percentage outcomes require a sample size of 70 (35 with each treatment) to provide a power of >80% with alpha = 0.05 to test for differences between these treatments. This was considered a reasonable sample to ascertain the effect size of the two treatments and to provide enough positive outcomes to evaluate time course for improvement with treatment and persistence of the treatment effect.

Breaking the blind

The randomization is in cohort blocks of 10, 5 with each treatment. The blind for the form of initial treatment will be broken for every cohort of 10 treated patients after all members of a cohort have completed the study. The blind may also be broken for specific subjects if the treatment information is needed for medical care of the patient.

Concomitant Medication

Permitted Medications

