Change in hemoglobin and iron parameters for all subjects and by group are shown in Table 3. The mean change in hemoglobin from baseline to follow up was 1.2 (SD 1.3) for Group A and 6.0 (17.2) for Group B. The mean change in Ferritin from baseline to follow up was 200.3 and 23.3 for Group A and Group B, respectively. The mean change in TSAT from baseline to follow up was 16.5 and 12.2 for Group A and Group B, respectively. The mean change in MCV from baseline to follow up was 24.2 and -17.6 for Group A and Group B, respectively. There was a significant difference between follow up ferritin and TSAT values. Group A had a higher follow up ferritin values ($p=0. <0.0001$) and higher TSAT ($p=0.007$) values compared to Group B.

Table 4 shows the changes in patient severity scores from baseline to follow up, and the follow up patient and clinical global impression scores for all subjects and by group. No significant differences between the 2 groups in terms of change in (1) patient severity score from baseline to follow up, (2) follow up patient global impression score, or (3) clinical global impression score were observed.

Table 5 shows the change in FSS from baseline to follow up. There were no significant differences between the 2 groups in terms of change in FSS.

Table 6 shows the change in IRLS score from baseline to follow up for all subjects and by group. Group B had a greater reduction in IRLS score from baseline to follow up compared to Group A

NOT SURE IF/HOW YOU WANT TO PRESENT THE ADVERSE REACTION DATA

Commented [VS1]: These are results from my original analysis. I still need to double check the results. However, before doing so, I want to confirm that there are no new data to analyze.

Commented [VS2]: Will define "Group A" and "Group B" once I know which group is which

TABLES**Table 1. Baseline hemoglobin and iron parameters for all subjects and by group.**

	Total	Group A	Group B	P-value¹
Hemoglobin	N=93	N=47	N=46	0.14
Mean (SD)	11.1 (1.5)	11.3 (1.3)	10.8 (1.6)	
Median (IQR)	11.6 (10.2, 12.2)	11.7 (10.8, 12.3)	11.6 (9.7, 12.1)	
Min, Max	7.0, 13.1	7.2, 13.1	7.0, 13.0	
Ferritin	N=91	N=45	N=46	0.017
Mean (SD)	17.9 (16.7)	22.6 (19.6)	13.5 (12.1)	
Median (IQR)	11.0 (7, 24)	19 (7, 29)	10.0 (7-15)	
Min-Max	3, 102	4, 102	3.0, 59.0	
TSAT	N=92	N=46	N=46	0.025
Mean (SD)	10.4 (6.2)	11.4 (5.9)	9.5 (6.5)	
Median (IQR)	9.0 (6, 13)	10.0 (8, 15)	8.5 (6.0-11.0)	
Min-Max	2, 36	2, 36	2, 32	
MCV	N=93	N=47	N=46	0.233

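### The effect size named as the primary goal is taken from response within each iron arm; it should be the randomised IV-minus-oral difference with a confidence interval

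*Protocol*

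**What the plan says.** The protocol's Rationale for study says of the two treatments that "we do not know the actual effect size of either treatment", and concludes: "The primary goal of the study is, therefore, to assess effect size". In the same paragraph: "Evaluating differences between the treatments is a tertiary goal of this study". The next paragraph explains the absence of a placebo group: "The decision not to do a placebo control is based on the assumption that the treatment effect size can be adequately determined without a placebo". That assumption is repeated at the end of the SAP's Introduction.

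The protocol's Statistical Analyses section defines the estimator: "The percentage responding will be evaluated for each drug condition to determine overall effect size at 6 weeks after treatment". For the IRLS and the PGI it uses change from baseline; for the CGI it uses the proportion scored 1 or 2. No control term enters.

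Primary objective 1 asks for the relative effect sizes of IV and oral iron. The first tertiary/exploratory objective is: "Evaluate significance of efficacy differences if any between oral and IV iron treatments at 6 weeks after treatment". For that comparison the protocol plans an unequal-variance t-test and a Fisher exact test.

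The title calls the study a "randomized, placebo-controlled comparator trial of IV vs oral iron treatment of RLS". Under Study Design and Dosing, however, saline and vitamin C serve only to mask which form of iron a patient gets. Every patient receives active iron.

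**The concern.** Change from baseline on patient- and clinician-rated scales is a total. It contains whatever iron does, plus natural fluctuation of symptoms, regression to the mean in patients selected for having RLS (the SAP's criteria add an IRLS score above 15), and expectation from two infusions and six weeks of pills. Without a group free of active iron, the design cannot split that total.

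The protocol's Rationale for study says that benefit in RLS with iron deficiency anemia has never been shown in a prospective controlled trial. The placebo-controlled support it cites is for RLS without anemia. If within-arm change is reported as the effect size, the trial will appear to fill that gap without having done so. The quantity it can estimate without this problem, IV minus oral, has no planned estimate or interval.

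**Working it through.** **1. The plan's own figure.** Inputs from Sample Size: 80% response on IV, 50% on oral, 35 per arm, alpha 0.05, power above 80%.

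- SE of the difference, unpooled = sqrt(0.8×0.2/35 + 0.5×0.5/35) = sqrt(0.01171) = 0.1082.
- Two-sided power = Φ(0.30/0.1082 − 1.96) = Φ(0.81) = 79%.

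This reproduces the stated figure approximately. It also shows that the sample size was built on the IV-oral contrast. (Under the planned Fisher test, two-sided, power is about 69%. That is a separate matter and nothing here depends on it.)

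**2. What each quantity identifies.** Let p0 be the response that would occur without active iron. The documents give no value, so the range is an assumption.

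| Assumed p0 | Net IV (80 − p0) | Net oral (50 − p0) | IV − oral |
|---|---|---|---|
| 0% | 80 | 50 | 30 |
| 10% | 70 | 40 | 30 |
| 20% | 60 | 30 | 30 |
| 30% | 50 | 20 | 30 |
| 40% | 40 | 10 | 30 |
| 50% | 30 | 0 | 30 |

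The same observed percentages fit a net oral effect anywhere from 50 points to none. The difference does not move.

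**3. Precision at 35 per arm.**

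- 28/35 (80%): exact 95% CI about 63% to 92%.
- 17/35 or 18/35 (about 50%): lower limit 31% for 17, upper limit 69% for 18.
- Difference: 30 ± 1.96×10.8 points, about 9 to 51 points.

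The first two intervals describe total response and carry none of the uncertainty about p0. The third is valid whatever p0 is.

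**4. The same structure in the SAP's draft Table 6 (IRLS change).** Group A −8 (SD 7.7, n=37); Group B −12.2 (SD 9.5, n=36).

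- These are total changes.
- The between-group difference is 4.2 points, SE = sqrt(7.7²/37 + 9.5²/36) = 2.03, 95% CI about 0.2 to 8.2.

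This only illustrates the form of the result. A comment in the SAP says the results still need checking, the total N is 74 while the groups sum to 73, follow-up ranges from week 1 to week 6, and the groups are not identified.

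**5. One component, under assumptions.** Regression to the mean from an IRLS cut at 15 is (1 − r)×SD×φ(z)/(1 − Φ(z)), with z = (15 − mean)/SD. Assumed population mean 18 to 22, SD 6 to 8, test-retest correlation r 0.6 to 0.8.

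- Smallest (mean 22, SD 6, r 0.8): 0.28 points.
- Largest (mean 18, SD 8, r 0.6): 1.84 points.

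Against the draft changes that is 0.28/12.2 = 2% to 1.84/8 = 23%. The cut appears in the SAP's criteria and not in the protocol's. The documents give no basis for a figure for natural course or expectation.

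**6. Is the contrast already estimated?** The protocol names two tests and no difference with an interval. The SAP's Statistical analysis section covers laboratory values only. SAP Tables 4 and 6 give group summaries and p-values, with no between-group difference, no CI and no responder percentage.

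**The case against.** Much can be said for the plan. Primary objective 1 says relative, the primary exploratory hypothesis is that IV exceeds oral, and the sample size rests on that contrast. The tertiary item in the objectives list concerns significance, and ranking tests low is reasonable in a pilot whose authors say the power figures are not accurate. The SAP has no tertiary label, names two co-primary outcomes and draws only between-group conclusions about RLS outcomes. The missing placebo group is openly stated as an assumption.

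All of this stands. It shows a plan that is inconsistent with itself: objective 1 points to the contrast, while the rationale calls evaluating differences tertiary and the analysis section computes effect size arm by arm. Disclosing an assumption does not support it.

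Two stronger readings should be set aside. A reader might infer that the next trial would be mis-sized. The successor named in the rationale is a larger study of IV-oral differences, and blinded within-arm response rates and SDs are legitimate inputs for sizing it. They would mislead only a comparison against no iron, which neither document plans.

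A reader might also infer that no repeated baseline exists. The protocol's Subject schedule provides telephone evaluations before treatment, and its section on RLS clinical evaluations has the IRLS and PGI-1 taken at every visit and call. More than one pre-treatment score is therefore possible, and the schedule appendix is not in the available text. Repeated scores would help with regression to the mean but not with natural course or expectation.

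**Conclusion.** The point holds in this form: within-arm responder percentage and change from baseline cannot serve as treatment effect sizes in a trial where both arms receive iron, and the assumption that they can is unsupported. Across an assumed non-iron response of 0 to 50%, each arm's net effect is undetermined over a 50-point span, while the 30-point planning difference is unaffected. This rests on the design and needs neither the Table 6 figures nor the regression-to-the-mean range. Overstatement is the likely direction of the error, not a proven one.

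The protection of the contrast assumes that the blind held and that missing outcomes do not differ by arm. Table 6 covers 37 and 36 patients, against 47 and 46 with a baseline hemoglobin in Table 1.

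The SAP's Results say "Group B had a greater reduction in IRLS score from baseline to follow up compared to Group A", while mean ferritin rose by 200.3 in A and 23.3 in B. A reader might infer that improvement did not track iron and was therefore nonspecific. The documents do not support that: the output is unverified, the groups are undefined and differed in baseline ferritin, median hemoglobin gains were similar (1.4 and 1.7), and the rationale itself leaves open whether the RLS follows the anemia or the low iron.

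**What to change.** In the protocol's Rationale for study, Study Objectives and Statistical Analyses, and in the SAP:

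- State that the effect size under primary objective 1 is IV minus oral at week 6: the risk difference for response (CGI score 1 or 2) and the difference in mean IRLS change, each with a 95% CI. Significance testing may stay exploratory.
- Report each arm's responder rate and change as *observed response on treatment*, stating that it is not an effect against no iron. These figures may still inform planning of an IV-versus-oral trial.
- Delete the assumption that effect size can be determined without a placebo, or limit it to the relative effect.

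The cost is wording and two intervals, with no added patients, arm or visits. The downside is that the trial could make no absolute efficacy claim for either form of iron. Aligning the title with the double-dummy active comparison would be a clerical follow-on.

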Placebo: Normal Saline will be administered following exactly the same procedure as that for IV iron.

Agent and administration for oral iron and placebo

Oral iron: This study will use Ferrous sulfate 325 mg tablets. The medication is to be taken together twice a day. If significant stomach distress occurs the patient may elect to take the medication with food and must then notify the research coordinator. The pills will be provided in opaque bottles with exactly enough for 7 weeks and a pill count will be made at the 6-week follow up to determine compliance. The oral pills will be stopped at the 6-week evaluation time.

Placebo: Standard vitamin C 250mg, given in the same bottle as the oral iron.

Subject schedule: (See appendix for chart of visits)

There will be 2 – 3 visits at the [name] clinic and telephone evaluations conducted by the Hopkins doctors prior to the start of treatment. After the first IV treatment there will be a telephone evaluation at 1, 2 and 4 weeks later and a clinic visit for blood tests at 4 weeks after the first of the pairs of IV treatment and again at about 6 weeks after the first of the pair of IV iron treatments. At 6 weeks after treatment responders will continue in the study with telephone evaluations of their RLS symptoms and medications at about 3, 6, 9 and 12 months after the first IV treatment. At 6 weeks after treatment non-responders will be given the option of receiving the IV ferumoxytol following the same procedure as at the initial treatment with a 6-week period of observation except this will be open label. Both the patient and the coordinator will know that ferumoxytol was given at this repeat dosing. This option will be given only if the patient continues to meet all the inclusion/exclusion criteria for the study noted below, except they will not be excluded for their prior IV treatment in this study. Those receiving the repeat IV dosing at 6 weeks will follow all the same procedures used after the first IV dosing, e.g. telephone safety checks and RLS symptom evaluations at 24-48 hours, 1 week and 4 weeks after initial treatment and a repeat clinic visit at about 6 weeks after the first of the two repeated IV treatment. This 6-week clinic visit will repeat blood tests, adverse event reporting and clinical evaluation of the RLS. The responders to this repeated IV treatment will be followed for up to one year following the same procedures as responders. The non-responders will end the study at this point.

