Patients continuing in the one year follow up will be followed for RLS symptoms over the entire year. The telephone evaluation at 12 months after treatment will end the study for these patients. Appendix A provides a flow sheet of the subject's schedule.

Subject population

Subjects with diagnosis of RLS and iron deficiency anemia

Inclusion criteria:

1. Aged \geq 18 years
2. Diagnosis of RLS based on questionnaire and confirmed by Hopkins Telephone Diagnostic Interview conducted by [name] or [name]
3. Iron deficiency anemia defined as ID either ferritin < 20 mcg/l, Tsat $<19\%$, anemia Hgb < 13 for both males and females.
4. Willingness to use contraceptive to avoid pregnancy: Women have to be surgically sterile, post menopausal or use one of the following contraceptives during the whole study period and after the

18 July 2014

study has ended for at least 5 times plasma biological half-life of the investigational medicinal product: intrauterine devices or hormonal contraceptives (contraceptive pills, implants, transdermal patches, hormonal vaginal devices, or injections with prolonged release).

5. Willingness to participate and signing the informed consent form

Exclusion criteria:

A subject will not be eligible for inclusion in this study if they fulfill any of the following criteria:

1. Iron overload or disturbances in utilization of iron (e.g. haemochromatosis and haemosiderosis)
2. Decompensated liver cirrhosis or active hepatitis (ALAT > 3 times upper limit of normal)
3. Serum ferritin > 500 ng/mL or transferrin saturation >40 %
4. Active acute or chronic infections (assessed by clinical judgment that may be indicated by White Blood Cells (WBC) and C-Reactive Protein (CRP) when these are available)
5. Rheumatoid arthritis with symptoms or signs of active inflammation
6. Pregnant and nursing women
7. History of multiple allergies
8. Known hypersensitivity to parenteral or oral iron or any excipients in the drug products
9. Previous IV iron treatment for RLS
10. Other iron treatment or blood transfusion within 4 weeks prior to the screening or treatment visit
11. Planned elective surgery during the study
12. Current (past 4 weeks) use of drugs that treat RLS, e.g. opioids, alpha-2-delta anti-depressants, dopaminergics (dopamine promoters, dopamine antagonists/blockers)

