Our major problem in testing the treatment benefits for IDA-RLS for either oral or IV iron was not knowing the actual effect size of either treatment. We had as an initial estimates the effect sizes from clinical experience with oral and IV iron therapy for IDA-RLS. Thus, we set the sample size to give adequate power to differentiate IV from oral iron assuming these estimates, without knowing if the estimates were accurate. The decision not to do a placebo control is based on the assumption that the treatment effect size can be adequately determined without a placebo. The decision to use a blinded comparator trial was based on the assumption that we would see differences between the treatments.

METHODS

The study was a randomized, comparative, double-blind study to evaluate effect size and time course of treatment response for RLS-IAD over six weeks. Two medications and two placebos were used with equal random assignment to both groups:

1. *FCM group:* Oral vitamin C, 500 mg tablets taken twice a day (placebo pill) and Ferumoxytol intravenous (IV) 1020 mg in two divided doses over 15 minutes 2-7 days apart
2. *FeSO4 group:* Ferrous sulfate 325 mg (oral) tabs morning and evening and IV saline given over 15 minutes 2-7 days apart (placebo infusion)

IV ferumoxytol, 1020 mg was be offered to those not significantly responding (CGI-I scores less than much or very much improved) at 6 weeks after oral iron and still meeting all the requirements for entry to study.

All patients who presented to a single outpatient Hematology clinic for treatment for their iron deficiency anemia (IDA), completed the Cambridge-Hopkins diagnostic questionnaire (CDQ) as part of their routine clinical evaluation, which was not limited to its use in this study. Those identified by the questionnaire as having RLS were checked for meeting the other inclusion criteria. The research coordinator reviewed the responses to the questionnaire, their clinical history and recent blood values to ensure inclusion criteria were met. If all criteria were met, the research coordinator consented the

patient for enrollment in the study. After consenting, a protocol number was assigned and appropriate blood samples obtained. Diagnosis of RLS was then confirmed by Hopkins-Hening Telephone Diagnostic Interview (HTDI) conducted by [name] or [name].

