For oral iron, ferrous sulfate 325 mg tablets containing 65 mg of elemental iron were used. The pills were taken twice daily on an empty stomach. If significant gastrointestinal perturbation occurred the medication could be taken with food. The oral placebo was standard vitamin C 250 mg tablets given in the same bottle as oral iron.

Following the first IV infusion, telephone evaluations were performed at 7, 14 and 28 days. At four weeks after the first of the pair of IV treatment were completed, blood tests were performed to include hemoglobin concentration and iron parameters (serum iron, total iron binding capacity, serum ferritin, percent transferrin saturation). A six weeks after the first of the pair of IV treatment were completed, another clinic visit was scheduled so a CGI form could be completed by involved medical personnel. At 6 weeks, non-responders were given the option of receiving ferumoxytol as an open-label infusion. At the 6-week clinic visit, repeat blood tests (see above), adverse event reporting and clinical evaluation of the RLS was performed.

Inclusion criteria were as follows:

1. Aged \geq 18 years
2. Diagnosis of RLS based on CHDQ and confirmed by HTDI
3. International RLS Study Group Severity Scale (IRLS) score > 15 .
4. Iron deficiency anemia defined as ID either ferritin < 20 mcg/l, TSAT $< 19\%$, anemia Hb < 13 g/dL for both males and females.
5. Willingness to use contraceptive to avoid pregnancy: Women have to be surgically sterile, post menopausal or use one of the following contraceptives during the whole study period and after the study has ended for at least 5 times plasma biological half-life of the investigational medicinal product: intrauterine devices or hormonal contraceptives (contraceptive pills, implants, transdermal patches, hormonal vaginal devices, or injections with prolonged release).
6. Willingness to participate and signing the informed consent form

Exclusion criteria were as follows:

1. Iron overload or disturbances in utilization of iron (e.g. haemochromatosis and hemosiderosis)
2. Decompensated liver cirrhosis or active hepatitis (ALAT > 3 times upper limit of normal)
3. Serum ferritin > 500 ng/mL or transferrin saturation $> 40\%$
4. Active acute or chronic infections (assessed by clinical judgment that may be indicated by white blood cells (WBC) and C-reactive protein (CRP) when these are available)
5. Rheumatoid arthritis with symptoms or signs of active inflammation
6. Pregnant and nursing women

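### Protocol and SAP each give two conflicting rules for who may be offered open-label IV iron at week 6, and neither says how the arm stays concealed when the offer is made

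*Protocol*

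**What the plan says.** The offer is described five times.

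- Protocol, Study Design: to patients not much or very much improved on the CGI-2 "at 6 weeks after oral-iron treatment and still meeting all requirements for entry to study". No waiver is stated.
- SAP, Methods, after the list of the two treatment groups: the same group, "at 6 weeks after oral iron and still meeting all the requirements for entry to study".
- Protocol, Summary: "Non-responders at 6 weeks after treatment may, if they qualify, have an open-label IV iron treatment". No arm is named.
- Protocol, Subject schedule: "At 6 weeks after treatment non-responders will be given the option of receiving the IV ferumoxytol". No arm is named. All inclusion and exclusion criteria apply again, "except they will not be excluded for their prior IV treatment in this study".
- SAP, Methods, paragraph on evaluations after the first infusion: "At 6 weeks, non-responders were given the option of receiving ferumoxytol as an open-label infusion".

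Two entry criteria bear on this. Exclusion 9 is "Previous IV iron treatment for RLS". Exclusion 10 is "Other iron treatment or blood transfusion within 4 weeks prior to the screening or treatment visit". The Subject population section also requires iron deficiency (ferritin below 20 or TSAT below 19%) with hemoglobin below 13. The tablets stop at the week-6 evaluation. Item 6 of the Protocol's Study Endpoints adds that patients who stop the oral medication for adverse effects may qualify for repeat IV treatment.

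On blinding, the Protocol keeps the arm from the coordinator. It breaks the blind by cohort of 10 once all members have completed the study, or for an individual whose medical care needs it. The SAP says investigators and analysts stayed blind until the analysis was complete.

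**The concern.** The two wordings select different patients, and each document contains both, so this is a contradiction and not a missing detail. Three things depend on it:

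- which patients may receive a further 1020 mg of IV iron;
- whether the coordinator and raters can learn a patient's arm while the blind is meant to hold;
- who makes up the 12-month follow-up. Responders to the open-label course join it, and it serves the first secondary objective (duration of effective treatment).

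The Protocol's Statistical Analyses section describes duration for oral and IV iron but does not say where a patient belongs who was randomised to one treatment and then given open-label ferumoxytol.

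**Working it through.** The plan states no figure for this group, so there is none to reproduce.

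**1. Whom the waiver serves.** Oral-arm patients had saline infusions, so exclusion 9 does not touch them. The waiver has work to do only for IV-arm patients, or where staff do not know the arm. It fits the wording without an arm limit and does nothing under the oral-only wording.

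**2. Exclusion 10.** The window is 4 weeks = 28 days, and week 6 is day 42. The second infusion falls 2 to 7 days after the first (the Dosing section says 2 to 6).

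- IV arm: 42 − 7 = 35 to 42 − 2 = 40 days since the last ferumoxytol dose, outside the window.
- Oral arm, adherent: 0 days since the last tablet, inside the window.

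If study tablets count as other iron, exclusion 10 catches adherent oral patients and no IV patients, contrary to Study Design. If they do not count, it catches neither.

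**3. Ceilings on numbers.** Inputs are from the Protocol's Sample Size section: 35 per arm, response 50% oral and 80% IV.

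- Oral non-responders: 35 × (1 − 0.50) = 17.5
- IV non-responders: 35 × (1 − 0.80) = 7
- Both: 17.5 + 7 = 24.5, of which IV is 7 / 24.5 = 29%

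The Protocol calls these rates uncontrolled experience, so they are varied here by assumption. Oral response of 30% to 70% gives 24.5 to 10.5 non-responders, and IV response of 60% to 90% gives 14 to 3.5. The IV share then runs from 3.5 / 28 = 12.5% to 14 / 24.5 = 57%.

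**4. Re-qualification.** SAP Table 2 gives follow-up quartiles. Groups are unlabelled. Group A is assumed to be IV, because its mean ferritin rise is 200.3 against 23.3 in Group B.

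- Group A: the lower quartiles are 127.5 for ferritin and 20.5 for TSAT. At most a quarter can lie below each entry cut-off, so at most half can meet either one. Ferritin below 20 is far under its lower quartile, so the true share is probably much smaller.
- Group B: the ferritin lower quartile is 21, so at least three quarters no longer have ferritin below 20. Median TSAT is 16, so at least half still have TSAT below 19%. The hemoglobin upper quartile is 13.4, so at least a quarter fail the hemoglobin limit.

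Re-applying the criteria therefore removes some oral patients and probably most IV patients. These are whole-group values, and non-responders may differ.

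**5. Disclosure.** Under the oral-only wording, every offer identifies an oral patient: up to 17.5 / 70 = 25% of the sample. Unblinding is planned only when all ten in a cohort have finished, and for followed patients that is the month-12 call. No section says who applies an arm-specific rule.

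**The case against.** The strongest reply is that the Subject schedule is the detailed operating section and its rule can be run without knowing the arm. The Study Design sentence may then be a loose summary, and it does not say the offer is for oral patients alone. This has force. But the SAP, written in the past tense, repeats both wordings, so a reader cannot tell which was applied. The Appendix A flow sheet, which might help, is not in the text available to this review.

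Four stronger readings are tempting, and the documents do not support them.

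- **Exclusion 10 bars every oral non-responder.** This needs study tablets to count as other iron. The Protocol's concomitant-medication sections separate study drug from other iron, and item 6 of Study Endpoints fits poorly with a general bar. Patients who stopped tablets more than 4 weeks earlier would escape it in any case. On the other side, exclusion 10 lacks the explicit study-drug exemption found in those sections. The point is unclear, and no more than that.
- **Seven IV patients would receive a second course.** Seven is a ceiling, because each must again be iron deficient and anemic.
- **The primary endpoint is unblinded.** The week-6 CGI defines non-response, so the patient's own rating logically precedes the offer. The absence of an offer is ambiguous, since failing the entry criteria explains it equally well. Spill-over to ratings of others in an open block is possible, but the documents give no means of sizing it.
- **The oral-only wording is the true intent.** Nothing in either document ranks one wording above the other.

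The medical-care exception to the blind does not name this offer as such a case. It is also fair that rewording cannot change who was treated. Clear reporting still can show it.

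**Conclusion.** The contradiction is real and appears in both documents. At the plan's own rates the wordings reach at most 17 to 18 patients or at most 24 to 25, and the difference is at most 7 IV-arm patients. The true numbers are smaller by an amount the documents do not fix. If study ferrous sulfate counts under exclusion 10, adherent oral patients are barred, against Study Design.

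An arm-specific offer would conflict with the Protocol's Blinding and Breaking the blind sections and with the SAP's blinding statement. The week-6 comparison is not directly exposed for the patient receiving the offer. What is exposed is the rating of others in an open block of 10, and the later follow-up.

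The counts rest on 35 per arm and the assumed 50% and 80% response. The re-qualification argument rests on inferred group labels and on tables whose analyst notes that the results still need checking. The point deserves correction but does not by itself undermine the primary result.

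**What to change.** 1. Reconcile the Protocol's Summary, Study Design, Subject schedule, entry criteria and item 6 of Study Endpoints, and both SAP Methods paragraphs, into one eligibility rule. This review does not say which rule is right.
2. State which entry list is re-applied (the SAP adds an IRLS score above 15 that the Protocol lacks) and whether study oral iron counts under exclusion 10.
3. Require the week-6 ratings to be complete and locked before eligibility is discussed, and state how the arm stays concealed from the coordinator and raters. For patients already treated, report what was done.
4. Report which rule was applied and the number of open-label recipients by randomised arm.
5. In the 12-month duration description, show open-label recipients separately from responders to the randomised treatment.

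The cost is revised wording and a tabulation by arm. No new data are needed.
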